## D. Approach

**D.1. Participants.** 60 participants will be recruited for this study. Participants must: A.) be age 18-65, and B.) have a diagnosis of either BN or BED. Individuals will be excluded if they are 1) below a BMI of 17.5, 2) are already receiving treatment for an ED, 3) require immediate treatment for medical complications as a result of eating disorder symptoms, or 4) are experiencing other severe psychopathology that would limit the participants' ability to comply with the demands of the current study (e.g. severe depression with suicidal intent, active psychotic disorder). Participants will be screened by phone to assess preliminary eligibility. Phone screens will use questions from the Mini International Neuropsychiatric Interview (MINI) to assess psychiatric comorbidity and will be conducted by trained doctoral students, similar to procedures used successfully in our teams other NIH trials.

**D.2. Refining RRT for use during the COVID-19 pandemic.** In month 1, we will revise our existing RRT manual to facilitate delivery via videoconferencing software by applying "lessons learned" from our ongoing remote groups for R01DK117072. For example, we will add instructions to use video conferencing features such as breakout rooms to facilitate in-session experiential activities and whiteboards to facilitate 'real-time' collaborative problem-solving. We will also revise the content of the RRT manuals to provide guidance on ways to build and maintain social connections during the COVID-19 pandemic as in-person social contact is limited (e.g., connecting with neighbors on Facebook group, scheduling virtual game nights with friends, enhancing intimacy with romantic partners during at home dates, attending virtual happy hours with colleagues), and address disruptions in current relationships due to the pandemic (e.g., conflict due to the switch to telework/teleschool). Participants will be encouraged (though not required) to connect with each other outside of group using email, texting, and social networking platforms to enhance social support outside of weekly sessions.

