**D.5. Remote study procedures.** Study assessments and group therapy sessions will be conducted using an encrypted HIPAA-compliant version of Zoom videoconferencing software which we are currently using in several NIH-funded clinical trials during the stay-at-home orders. Informed consent will be collected using an electronic consent form that participants will be asked to complete during the appointment after reviewing the consent form jointly with a staff member.

**D.6. Assessments.** Assessments will be conducted by blinded assessors at baseline, mid-treatment (after session 5), post-treatment (after session 10), and at a 3-month follow-up. Our assessment strategy was specifically designed to allow for remote assessment during the COVID-19 pandemic and thus will only include measures that can be completed using videoconferencing or via the participants home computer. In order to maximize assessment completion, we will increase compensation across assessments (\$50, \$75, \$100, \$125).

**D.6.1. Feasibility and Acceptability.** Assessment of feasibility will include % of eligible patients enrolled, attrition, and study retention. We will use a Feedback Questionnaire (FQ) to obtain qualitative acceptability ratings, which will be modified from FQs used in our prior intervention development projects.

**D.6.2. Primary outcomes.** The Eating Disorder Examination is a widely utilized, semi-structured interview for the assessment of eating disorder symptoms. We will use number of binge episodes in the last 28 days and EDE global scores as the primary outcomes. Remission status will also be evaluated at each assessment following the baseline assessment and will be defined as the absence of any binge episodes or compensatory behaviors in the 28 days prior to the assessment point and an EDE global score within 1 standard deviation of the community norm (EDE global <1.74).

**D.6.3. Secondary outcomes.** We chose to use commonly-used and well-validated measures of depression (Beck Depression Inventory-II), substance use (Alcohol, Smoking, and Substance Involvement Screening Test), and quality of life (Quality of Life Inventory) to assess secondary outcome measures.

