## STATISTICAL DESIGN AND POWER

Descriptive statistics and exploratory graphing will be generated for all variables of interest measured at all time points (i.e., baseline, mid-treatment, post-treatment, 3-month follow-ups). Data summaries will be produced both for the combined sample, and separately by treatment condition. Variables will be transformed if necessary using Box-cox power transformation. Baseline characteristics will be compared between treatment conditions using ANOVA (or non-parametric Kruskal Wallis test, as appropriate) for continuous variables and a chi-square test for categorical variables. Key baseline variables that differ by condition will be considered for use as covariates in the analyses described below.

**Primary Aim 1.** To assess feasibility and acceptability, we will use the following benchmarks: (a) recruitment success: enrollment of 60 patients; (b) attrition: retention of >75% of patients through all assessments; (c) study retention: patients attend at least 90% of all treatment groups; (d) satisfaction: patients express high satisfaction with RRT based on feedback questionnaires.

**Primary Aim 2.** To evaluate the effect of each treatment condition on hypothesized targets, we will model the pattern of change in reward response to palatable food, reward response to day-to-day life activities, social isolation, and loneliness separately over time using multilevel models (PROC MIXED in SAS). The first level will model individual participant's score on the relevant target over time with baseline as time 0. At the second level, the individual intercept and slope will be entered as outcomes with treatment condition as a predictor. We will examine each treatment condition separately. The cross-level interaction between time and treatment condition will be used to determine the effect of treatment condition on the pattern of change in the hypothesized targets. Restricted maximum likelihood will be used to estimate model parameters and to test the significance of random effects. Both linear and higher-order time effects will be examined based on model selection criterion such as Akaike Information Criterion (AIC) and Bayesian Information Criterion (BIC). With the fitted multilevel model structure, statistical contrasts will be performed at mid-treatment, post-treatment, and 3-month follow-up.

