**Primary Aim 3.** Analyses will be conducted via linear mixed effects models for longitudinal data, which increase power by fully exploiting the strong correlation in treatment outcomes of interests (i.e., percent binge frequency reduction and percent change in EDE global eating pathology) across time. Patterned covariance matrices as implemented in (PROC MIXED in SAS) and will be used to evaluate between group differences for percent binge reduction and percent change in EDE global eating pathology across the study as a whole, and at each assessment post-baseline. Separate variance components will be used to capture therapist and participant-within-therapist variation. The within-subject covariance matrix will be assumed common across study arms, with an exponential variance function to deal with heteroscedasticity and a continuous-time AR(1) correlation matrix to accommodate residual autocorrelation over the unequal-size time intervals between follow-ups. Outcomes at all four time points will be estimated jointly for maximum statistical efficiency in the presence of intermittent missingness and loss to follow-up. The model will include random effects for subject and time (with higher-order effects if needed to capture nonlinear change), and fixed effects for treatment arm, time by treatment interaction, demographic information, and baseline values of binge frequency and global eating pathology. Time-specific covariate-adjusted contrasts will be used to compare outcome between groups.

**Secondary Aim 1.** We will use the same analytic approach described above for Primary Aim 3 but will test the impact of treatment condition on secondary outcomes including depression, substance abuse, and quality of

life.

**Attrition.** Patterns of missing data will be examined. Likelihood-based estimation methods and multiple imputation models will be used to handle missing data. In addition, we will use Hedeker and Gibbons' procedure to examine if dropouts influence the multilevel model results. If the missingness mechanism is related to the missing outcome itself, we will use sensitivity analyses to explore how robust our findings are with respect to a range of assumptions regarding missing data.

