**Power analyses.** Using the method described by Raudenbush and implemented with the software Optimal Design, power calculations were made for mixed effects models. A sample size of 154 (77 for each condition) is required for 80% power to detect a medium effect with the significant level of 0.05 and four assessment points, assuming the ratio of the variability of level-1 coefficient to the variability of level-1 residual is one. Fritz and MacKinnon documented sample size requirements to guarantee 80% power at the significance level of 0.05 for mediation models. Under the assumption of a medium effect for intervention with the mediator and a medium effect for the mediator on outcome controlled for intervention, the required sample size is 72 in total with 36 per intervention arm to achieve 80% power in simple mediation models. Given our relatively small sample size ( $n=60$ ), our study is powered to detect large effect sizes. While we observed large effect sizes in our pilot trial of RRT compared to a wait list control, we anticipate that the effect sizes may be smaller in the current trial as supportive therapy is an active treatment condition. It is likely that we may be underpowered for formal tests of statistical significance in this preliminary study. We will rely on effect sizes for interpretation when underpowered.

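### SAP Primary Aim 3 analyses percent change where the protocol names a binge count and an EDE score, and for binge counts the percent scale is a poor choice with no rule for zero or low baselines

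*SAP*

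**What the plan says.** Protocol D.6.2 fixes the primary outcomes: "We will use number of binge episodes in the last 28 days and EDE global scores as the primary outcomes". It mentions neither change scores nor percentages. Remission, in the same section, is also defined on absolute counts and scores.

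SAP Primary Aim 3 uses other variables. It justifies mixed models by the correlation "in treatment outcomes of interests (i.e., percent binge frequency reduction and percent change in EDE global eating pathology) across time", and says that the models "will be used to evaluate between group differences for percent binge reduction and percent change in EDE global eating pathology". It adds that "Outcomes at all four time points will be estimated jointly for maximum statistical efficiency", and its fixed effects include "baseline values of binge frequency and global eating pathology".

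Protocol D.1 requires that participants "have a diagnosis of either BN or BED" and states no minimum number of episodes in the 28-day window. The SAP gives no formula for percent reduction and no rule for a zero or small baseline. Its only general provision is in the opening paragraph: "Variables will be transformed if necessary using Box-cox power transformation".

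**The concern.** The two documents name different analysed variables for the same primary outcomes, and nothing says which governs. The SAP's mediation analysis refers only to the primary outcomes, so it inherits the ambiguity. An analyst could settle the scale after seeing data.

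For binge counts the scale chosen in the SAP is also the weaker one. A ratio to a single baseline count is undefined at zero, very sensitive when the count is small, and asymmetric between improvement and worsening. A handful of patients can then determine the arm contrast. The SAP's power section expects the trial to be underpowered and says interpretation will then rest on effect sizes. A scale that shrinks or destabilises the standardised effect therefore bears on whether a full trial looks worthwhile.

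**Working it through.** **1. The plan's own figure.** The SAP states: "A sample size of 154 (77 for each condition) is required for 80% power to detect a medium effect", with four assessments, alpha 0.05 and a variance ratio of 1. Assume that medium means d = 0.5, the test is two-sided and the occasions are equally spaced.
- The centred times are -1.5, -0.5, 0.5 and 1.5, with sum of squares 5. The slope variance is therefore 1 + 1/5 = 1.2 in units of the true slope variance.
- Normal approximation: n per arm = 2 x 1.2 x (1.960 + 0.842)^2 / 0.5^2 = 75.4, so 76.
- Noncentral t: power is 0.798 at 76 per arm and 0.8035 at 77, so 77 per arm and 154 in total. The figure reproduces.

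This calculation uses a standardised effect and names no outcome scale, so it does not show which variable is meant. Changing the variable alters no stated number.

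**2. Arithmetic of the percent scale.** Percent reduction = 100 x (baseline - follow-up) / baseline.
- 40 to 10 episodes: 100 x 30/40 = 75%.
- 2 to 8 episodes: 100 x (2 - 8)/2 = -300%.
- The mean of these two scores is (75 - 300)/2 = -112.5%, although total episodes fell from 42 to 18, a reduction of 24/42 = 57%.
- In an arm of 30, one score of -300% moves the arm mean by 300/30 = 10 percentage points compared with a score of 0.
- Three extra episodes are a 300% increase from a baseline of 1, 150% from 2, 75% from 4, 19% from 16 and 11% from 28.

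**3. Zero baselines.** The documents give no count distribution. Assume Poisson counts with the same rate in all 60 patients.

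| Assumed rate per 28 days | P(count = 0) | P(at least one of 60) |
|---|---|---|
| 2 | 13.5% | about 100% |
| 4 | 1.8% | 67% |
| 8 | 0.03% | 2% |
| 12 | 0.001% | <0.1% |

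A current diagnosis makes the upper rows unlikely for most patients, but no entry rule excludes them.

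**4. Box-Cox.** The transformation needs positive values. Percent reduction is zero or negative for anyone who does not improve. Recast as follow-up/baseline, it is zero for anyone free of binges at follow-up. A shift is needed, and the SAP states none.

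**5. Baseline as a time point.** Percent change at baseline is 0 for every patient, with no variance. Modelling all four time points jointly therefore includes one constant outcome, while the baseline value is also a covariate.

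**6. Simulation.** All runs use 30 per arm, one follow-up visit and least squares adjusted for baseline, with assumed distributions.

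*Set A*: gamma-Poisson counts, mean 8 or 16, follow-up rate 60% of baseline (control) against 25% (RRT), 1,500 trials per scenario. Baseline counts have only Poisson noise around each patient's rate.

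| | Minimum baseline 1 | Minimum baseline 4 |
|---|---|---|
| Median worst patient (increase) | 190-350% | 167-227% |
| Share of outcome variance, top 3 of 60 | 52-61% | 49-55% |
| Power, percent | 0.59-0.73 | 0.71-0.77 |
| Power, log(count + 1) | 0.66-0.72 | 0.69-0.73 |

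Null rejection was 0.04-0.05 (percent) and 0.05-0.06 (log).

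*Set B*: median rate 12 or 16, log-SD 0.6-0.8, negative binomial noise at each visit (dispersion 1.5 or 3), follow-up rates 0.6 against 0.3 of baseline, 600 trials per scenario.

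| | Percent | log(count + 1) |
|---|---|---|
| Power, minimum baseline 1 | 26-53% | 56-83% |
| Power, minimum baseline 4 | 44-73% | 62-87% |
| Median standardised effect, minimum 1 | 0.38-0.54 | 0.57-0.80 |
| Null rejection | 3-6% | 4-8% |

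*Dispersion varied*, minimum baseline 4: the power gap was 14-18 points at dispersion parameter k = 2, 6-8 points at k = 5 and 0-1 point for Poisson counts. A larger k means less noise. Across further runs of this kind, 3 of 60 patients carried 38-70% of the residual variance.

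Simulation error on a power near 60% is sqrt(0.6 x 0.4/1500) = 1.3 points in Set A and sqrt(0.6 x 0.4/600) = 2.0 points in Set B.

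**The case against.** The percent outcomes are computed from the protocol's own EDE measures, so instrument and construct are unchanged. The SAP also promises descriptive summaries of all variables at every time point, and remission uses absolute values. This stands: a reader might infer that the trial would report a different endpoint altogether, but the disagreement is about the analysed variable.

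Other stronger readings also fail:
- *A patient with a zero binge baseline has no primary outcome.* EDE global remains available for that patient.
- *EDE global is equally unstable.* Nothing in the documents shows that baseline scores near zero are likely. Only the mismatch stands.
- *Box-Cox can do nothing.* A shifted transform of follow-up/baseline, such as log(ratio + 0.1), recovers much of the loss for non-zero baselines. With k = 2 and minimum baseline 1, power was 0.32-0.37 for raw percent, 0.57-0.64 for the shifted transform and 0.67-0.75 for log(count + 1). The valid criticism is that the SAP specifies neither a shift nor a zero-denominator rule.
- *Power is certainly lost.* Set A shows little difference, and at minimum baseline 4 it slightly favours percent.

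It is also fair that the simulations use one visit and ordinary least squares, not the SAP's repeated-measures model with an exponential variance function. That function might reduce the influence of extreme values, but the SAP names no covariate for it, and it cannot supply a value at a zero baseline.

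**Conclusion.** The mismatch between Protocol D.6.2 and SAP Primary Aim 3 is certain and needs no assumption. So are the undefined value at zero, the asymmetry, the absence of a handling rule and the constant baseline outcome.

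The size of the harm rests on assumed count distributions. In every scenario a few patients dominated: 3 of 60 carried roughly 40-70% of the variance. A floor of 4 on the baseline reduced this only modestly, so low baselines are not its sole cause. Loss of power and of standardised effect is material when within-patient overdispersion is large, and small or absent otherwise. The documents give no dispersion figure to decide between these. Type I error on the percent scale was not inflated.

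This should be fixed before unblinded analysis, but it does not invalidate a pilot that already expects limited power.

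**What to change.** In SAP Primary Aim 3, analyse the protocol's outcomes at mid-treatment, post-treatment and 3-month follow-up in the planned linear mixed model:
- log(28-day binge count + 1), with log(baseline count + 1) as covariate;
- raw EDE global score, with baseline score as covariate.

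Use baseline only as a covariate, and have the mediation analysis refer to the same variables. Report percent reduction from baseline descriptively, by arm, from group mean counts.

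Do not read exp(coefficient) from the log(count + 1) model as a rate ratio: a true ratio of 0.50 came out at about 0.53-0.60 in the simulations. If a rate ratio is wanted, take it from a sensitivity negative binomial mixed model. That needs a procedure other than PROC MIXED and a small-sample correction. An overdispersed Poisson model with model-based standard errors rejected 7-10% under the null at 30 per arm.

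The cost is SAP wording. Data, visits and the main procedure stay the same. The downside is a headline effect on a log scale, not a direct percentage.

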**A.5.3. Increasing the quantity and quality of social interactions.** When choosing pleasant events, RRT specifically encourages individuals to prioritize activities that are social in nature given evidence that these activities tend to be more enjoyable in the moment than solitary activities. Similarly, given that for most individuals, meaningful and fulfilling relationships are among the most important valued life domains, RRT particularly focuses on building valued life domains related to relationships (e.g. romantic relationships, family relationships, friendships). RRT also teaches skills focused on how to develop and maintain high quality relationships. These include strategies for making relationships deeper and more fulfilling, strategies for building intimacy in new relationships, and effective communication strategies. Because many individuals with EDs are socially isolated and the development of meaningful relationships will take time, RRT is delivered in a group format and encourages the use of the group as an immediate source of social connection. Group members are encouraged to develop relationships with each other outside of the group setting that may last well beyond the program’s short duration.

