## **A.7. Current study and specific aims.**

In the current study, we will revise our existing 10-session group RRT treatment manual to specifically address the challenges in building social support and enhancing both momentary and sustained reward during the COVID-19 pandemic (Preliminary Aim 1). In months 2-18, we will conduct a small pilot RCT that will randomize individuals to receive either 10-sessions of RRT (n=30) or supportive therapy (n=30), both delivered as group-treatments via videoconferencing software. The specific aims of the current study are to confirm the feasibility and acceptability of RRT for EDs (Primary Aim 1), evaluate the ability of RRT to engage critical targets including reward to day-to-day life activities, reward to palatable foods, social isolation, and loneliness (Primary Aim 2), and provide preliminary estimates of efficacy in reducing ED symptoms at both post-treatment and a 3-month follow-up (Primary Aim 3). We will also evaluate the impact of RRT on secondary outcome variables including depression, substance use, and quality of life (Secondary Aim 1).

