**D.3. Supportive therapy as an active control condition.** We considered several possible comparison conditions for the proposed trial including treatment-as-usual, the provision of self-help reading materials, and the use of a gold-standard comparison such as CBT before determining that a group-based supportive therapy condition was the best control condition for the current state of the research. Supportive therapy will allow us to control for many of the non-specifics of therapy such as working with an empathetic provider and instilling hope and optimism. The group-nature of the supportive therapy condition will also allow us to better determine whether treatment gains were due to the content of RRT or if comparable gains can be achieved by simply increasing social connection and support via a group treatment. The supportive therapy condition will be based on existing manuals. As is typical for supportive therapy conditions, the group leader will be instructed to be non-directive and allow the patients to determine the focus of each session. The group leader will be encouraged to use reflective listening, elicit and validate affect, and offer empathic comments. Group leaders will also be instructed to avoid any cognitive and behavioral techniques that could overlap with RRT.

**D.4. Treatment facility, clinicians, training, supervision, competence and fidelity.** All treatment for the study will be provided by clinicians from the WELL Center Clinic (see Facilities for more details), an outpatient community clinic serving the Philadelphia metropolitan area. Weekly clinical supervision will be provided throughout treatment by [name] who will remain unblinded to allow her to provide clinical supervision. To maximize fidelity, we will use treatment manual which are designed for easy use during group treatment sessions. All treatment groups will be audio recorded, and an independent evaluator (a doctoral student with intensive training) will independently monitor and rate treatment competence and fidelity for 25% of group sessions for both conditions.

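### Aim 3 models clustering by therapist but not by therapy group, so its intervals are too narrow if clinicians lead groups in both arms and of uncertain coverage if they do not

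*SAP*

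**What the plan says.** The efficacy model is in the SAP, Statistical Design and Power, under Primary Aim 3. Its clustering provision is one sentence: "Separate variance components will be used to capture therapist and participant-within-therapist variation". The remaining random effects are at patient level: "The model will include random effects for subject and time (with higher-order effects if needed to capture nonlinear change". Secondary Aim 1 adopts the same approach. Neither paragraph mentions the therapy group or a method for denominator degrees of freedom.

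Protocol A.7 describes the allocation as RRT ("n=30) or supportive therapy (n=30), both delivered as group-treatments via videoconferencing software"). Protocol A.5.3 makes the group part of the mechanism: "RRT is delivered in a group format and encourages the use of the group as an immediate source of social connection".

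On staffing, Protocol D.4 says only that "All treatment for the study will be provided by clinicians from the WELL Center Clinic". Protocol D.3, on the supportive therapy condition, adds that "Group leaders will also be instructed to avoid any cognitive and behavioral techniques that could overlap with RRT". Neither statement fixes a clinician to one arm or one group. Group size, number of groups, number of clinicians and any ICC are not given.

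**The concern.** Patients who share a group for ten sessions can be expected to have correlated outcomes, and in RRT the shared group is meant to matter. The plan accepts that clustering needs modelling but attaches it to the clinician. That is a safe stand-in for the group only under some staffing patterns, and the plan does not say which pattern applies.

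The pilot's purpose, stated in Protocol A.6, is to decide whether RRT is worth a fully powered trial. The SAP's power paragraph concedes that formal tests may be underpowered and turns to effect sizes. The width of the interval around each effect size is then the main protection against over-reading a chance difference between a handful of groups.

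**Working it through.** **Inputs from the documents.** N=60, 30 per arm; group delivery in both arms; "with the significant level of 0.05 and four assessment points" (two-sided assumed); therapist as the only cluster term.

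**Assumptions (not in the documents).** Groups of m = 5, 6 or 10, which gives 60/m = 12, 10 or 6 groups; group ICC of 0 to 0.10; medium effect taken as 0.5 and large as 0.8.

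**1. The plan's own figure.** The SAP states: "A sample size of 154 (77 for each condition) is required for 80% power to detect a medium effect". Using the linear-change power method with M=4 assessments and a variance ratio of 1:

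- V = 12/((M+1)M(M−1)) = 12/(5×4×3) = 0.20
- reliability = 1/(1+0.20) = 0.833
- noncentrality = N·d²·0.833/4 = 154×0.25×0.833/4 = 8.02, which on F(1,152) gives power of 80.3% (N=152 gives 79.8%)

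The figure reproduces with patients treated as independent, so it contains no allowance for clustering. At N=60 and d=0.8 the same method gives 79%.

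**2. Clinicians lead a group in each arm.** Let T clinicians each lead one group of m per arm. The clinician's effect enters both arm means equally and cancels from the difference. The true variance of the contrast is (2/T)(σ²_group + σ²_patient/m). With no group term, the model uses about (2/T)(σ²_group + σ²_patient)/m. The ratio is the design effect 1+(m−1)·ICC. At ICC 0.05:

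- m=5: 1+4×0.05 = 1.20; SE understated by a factor √1.20 = 1.10; effective N = 60/1.20 = 50
- m=6: 1.25; 1.12; 48
- m=10: 1.45; 1.20; 41

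For m=10, coverage of a nominal 95% interval is about 2Φ(1.96/1.204)−1 = 89.6%.

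**3. Each clinician leads one group in one arm.** Therapist and group are the same unit, so the therapist component estimates the variance that the contrast needs. What remains open is how well it is estimated from 6 to 12 clusters and which degrees of freedom are used.

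**4. Simulation.** Both patterns were simulated under the null (200,000 runs per case; one post-baseline contrast, balanced groups, normal outcome; model with arm and random therapist; REML variance truncated at zero). Type I error is 100% minus coverage:

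| Pattern | m | ICC 0.02 | ICC 0.05 | ICC 0.10 |
|---|---|---|---|---|
| Clinician in both arms | 5 | 6.3% | 7.9% | 10.6% |
| | 6 | 6.5% | 8.5% | 11.9% |
| | 10 | 7.4% | 10.8% | 16.6% |
| One clinician per group, patient-level df | 5 | 4.4% | 5.0% | 5.8% |
| | 6 | 4.5% | 5.3% | 6.3% |
| | 10 | 5.0% | 6.4% | 8.2% |
| One clinician per group, strict cluster-level df | 5 | 2.7% | 3.1% | 3.8% |
| | 6 | 2.3% | 2.8% | 3.6% |
| | 10 | 0.9% | 1.5% | 2.3% |

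At ICC 0, the first pattern gives 5.2-5.3%. Adding a therapist variance of 0.05 to that pattern changes coverage by less than one percentage point. With one clinician per group, the therapist variance is estimated as zero in about 23-49% of runs over ICC 0.02-0.10. If arm-specific clinicians lead two groups each, coverage is 91.9-95.8% with patient-level degrees of freedom and about 99-100% with cluster-level ones.

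**The case against.** A reader might infer that Aim 3 intervals are too narrow whatever the staffing. The documents do not support that. With one arm-specific clinician per group, the planned term already carries the group variance. Few clusters make that variance estimate unstable; they do not by themselves narrow the interval. The lower rows of the table run from clearly conservative to mildly anti-conservative, depending on the degrees of freedom, and the SAP names no method. This part of the objection stands and limits the point.

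It is also fair that nothing says clinicians cross arms. The instruction to supportive-therapy leaders to keep away from RRT techniques fits shared or separate staff equally well. Group size and ICC are assumptions too, and with small groups or an ICC near 0.02 the excess error in the crossed case is only one or two percentage points. Hence the results are given as a range.

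Finally, this is a pilot that leans on effect sizes, and the missing term leaves point estimates essentially unchanged. That makes rejection rates less important here. It does not make interval width unimportant, because the same understated SE sets both.

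**Conclusion.** The point holds in conditional form. Therapist is the only cluster unit in a model for two group-delivered arms, and the plan does not give the mapping that would make it adequate.

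- **Clinicians lead groups in both arms:** intervals are too narrow whenever the group ICC is above zero. Type I error is about 6-7%, 8-11% and 11-17% at ICC 0.02, 0.05 and 0.10 for groups of 5 to 10, and essentially nominal at ICC 0.
- **One clinician per group, one arm each:** coverage is uncertain rather than clearly too low. Error is about 5-6.5% at ICC 0.05 and 6-8% at 0.10 with patient-level degrees of freedom, and about 1.5-4% with strict cluster-level ones.
- **One clinician per arm:** therapist is fully confounded with arm and the component cannot be estimated.

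These sizes rest on the assumed group sizes and ICCs and on a single-time-point simulation with balanced groups. The change is cheap and should be made, but the documents do not demonstrate that the intervals will be wrong.

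**What to change.** In Primary Aim 3 and Secondary Aim 1:

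1. State how clinicians and therapy groups map to arms.
2. Replace the therapist sentence with a random effect for therapy group, with participant nested within group, and add a therapist effect where a clinician leads more than one group.
3. Specify Kenward-Roger degrees of freedom (DDFM=KR in PROC MIXED) for all arm contrasts.

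The cost is SAP wording and one group identifier in the dataset. The group variance will be imprecise and often estimated as zero. With 3 or 4 clinicians crossing arms, the group-adjusted contrast has only 2-3 degrees of freedom, the variance was zero in about 35-48% of simulated runs, and type I error was 4.4-6.5%. Intervals will usually be wider and closer to nominal coverage, though not exactly at it. Even an imprecise group variance is useful for planning a later group-delivered trial.
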